7.1 Treatments to be administered

Each subject will receive nifurtimox oral tablets three times daily for 60 days, or for 30 days followed by nifurtimox placebo administered three times daily for 30 days.⁹⁸

Each nifurtimox tablet contains either 30 mg or 120 mg of nifurtimox as the active ingredient, and the following excipients: calcium hydrogen phosphate dehydrate, maize starch, silica colloidal anhydrous, and sodium lauryl sulfate.

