7.3 Treatment assignment

Subjects will be randomized via IVRS/IWRS to one of two treatment groups in a 2:1 ratio (60-day regimen vs. 30-day regimen) as follows:

- Nifurtimox tablets administered three times daily for 60 days (Days 1 60, active nifurtimox treatment, Treatment Group 1), or
- Nifurtimox tablets administered three times daily for 30 days, followed by nifurtimox placebo administered three times daily for 30 days (Days 1 30, active nifurtimox treatment; Days 31 60, placebo; Treatment Group 2).

⁹⁸ Last sentence deleted since it appears later in Section 7.4 (Amendment 1)

⁹⁹ Text modified for clarity (Amendment 1)

	Integrated Clinical Study Protocol BAY A2502 / 16027	
03 NOV 2020	Version 11.0	Page: 43 of 259

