¹⁰⁴ Table 7-1, Table 7-2 and associated text in dosage and administration modified as of amendment 2

¹⁰⁵ In this column, upper limit of weight ranges in each category changed per the most current dosing information (Amendment 1)

	Integrated Clinical Study Protocol	
	BAY A2502 / 16027	
03 NOV 2020	Version 11.0	Page: 44 of 259

At Visits 2 and 6, when study drug is dispensed, subjects/legally authorized representatives will be provided with a diary on which to document the date, exact time, and doses (morning, noon, and night) of study drug, and comments (see Section 1). Should a subject vomit or spit out study drug, the occurrence will be recorded on the diary along with the time of the event.¹⁰⁶ Subjects/legally authorized representatives will be instructed to bring their diaries with them to each in-clinic study visit. The diaries will be collected and reviewed at each study visit to perform drug accountability and assess treatment compliance.¹⁰⁷

Riboflavin is included as a colorant in the matching placebo tablets for study drug blinding purposes. A common side effect of riboflavin ingestion is bright yellow urine. Subjects and/or their legally authorized representatives will be advised of the possibility of change in the subject's urine color within the informed consent form, and when study drug is administered and dispensed at the investigational site.¹⁰⁸

Subjects consenting to optional PK assessments must withhold taking the morning dose of study drug on the day of Visits 3, 6, and 8, when pre- and post-dose PK blood samples will be obtained. Subjects not consenting to optional PK assessments may take their study drug on the mornings of Visits 3, 6, and 8 as instructed.¹⁰⁹

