9.6 Safety

9.6.1 Adverse events

9.6.1.1 Definitions

Definition of adverse event (AE)

In a clinical study, an AE is any untoward medical occurrence (i.e., any unfavorable and unintended sign [including abnormal laboratory findings], symptom, or disease) in a patient or clinical investigation subject after providing written informed consent for participation in the study. Therefore, an AE may or may not be temporally or causally associated with the use of a medicinal (investigational) product.

A surgical procedure that was planned prior to the start of the study by any physician treating the subject should not be recorded as an AE (however, the condition for which the surgery is required may be an AE).

In the following differentiation between medical history and AEs, the term "condition" may include abnormal physical examination findings, symptoms, diseases, laboratory, or ECG.

- Conditions that started before signing of informed consent and for which no symptoms or treatment are present until signing of informed consent are recorded as medical history (e.g., seasonal allergy without acute complaints).
- Conditions that started before signing of informed consent and for which symptoms or treatment are present after signing of informed consent, at unchanged intensity, are recorded as medical history (e.g., allergic pollinosis).
- Conditions that started or deteriorated after signing of informed consent will be documented as AEs. This includes intercurrent illnesses.

¹⁶⁴ Text modified for clarity (Amendment 1)

¹⁶⁵ Text modified as per amendment 4

	Integrated Clinical Study Protocol	
	BAY A2502/ 16027	
03 NOV 2020	Version 11.0	Page: 68 of 259

Definition of serious adverse event (SAE)

An SAE is classified as any untoward medical occurrence that, at any dose, meets any of the following criteria (a - f):

- a. Results in death
- b. Is life-threatening

The term 'life-threatening' in the definition refers to an event in which the subject was at risk of death at the time of the event, it does not refer to an event which hypothetically might have caused death if it were more severe.

c. Requires inpatient hospitalization or prolongation of existing hospitalization

A hospitalization or prolongation of hospitalization will not be regarded as an SAE if at least one of the following exceptions is met:

- The admission results in a hospital stay of less than 12 hours
- The admission is pre-planned

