Safety variables will be summarized by means of descriptive statistics and/or frequency tables as appropriate. Summaries will be given by treatment regimen. All post-treatment AEs and SAEs, as well as drug-related AEs and SAEs, will be summarized by MedDRA terms.¹⁹⁰ AEs occurring between the time of consent and the first dose of study drug will be summarized separately. Subjects experiencing urine discoloration from riboflavin ingestion will be listed also, although these incidences will not necessarily be considered AEs.

¹⁸⁴ Text deleted per Modification 2 (Amendment 1)

¹⁸⁵ Text modified as of amendment 2

¹⁸⁶ "Exploratory" added per Amendment 5.

¹⁸⁷ Text modified/added for clarity (Amendment 1)

¹⁸⁸ Sentence added per Amendment 5.

¹⁸⁹ Replaced IFA with IHA per Amendment 6.

¹⁹⁰ Text modified as of amendment 2

03 NOV 2020 Version 11.0

Missing data/drop outs

No imputations will be made for missing data due to dropouts or other causes. For the primary efficacy analysis done on the FAS, a patient without an assessment at the primary 12 month time point will be considered a treatment failure. For the secondary analysis using the PPS, patients who do not have serology determinations to assess the primary endpoint will be excluded from the analysis.

The following sensitivity analyses for the primary efficacy variable will be performed:

• Missing values due to the following reasons treated as treatment failures and other missing values excluded from analysis:¹⁹¹

1. the reason for discontinuation is known or suspected to be treatment ineffectiveness or an AE

2. a subject has not had a negative serology at any visit and has no serology determination for the primary analysis visit

3. an indeterminate or incorrectly performed serology determination occurs at the primary analysis visit.¹⁹²

- Observed data only
- Analysis on PPS

Pharmacokinetic data

Specifications for PK data analysis will be provided in a separate document. Plasma concentration vs time data documented within the study report will be analyzed descriptively using univariate statistics.¹⁹³

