## **Adverse Events**

All adverse events occurring during the study (i.e., from signing of informed consent until last visit) will be reported. The MedDRA coding system will be used to code the adverse events.

An overview of frequencies of subjects who died, experienced any adverse event, experienced any drug-related adverse event, experienced a serious adverse event (SAE), experienced a drug-related serious adverse event, or discontinued due to an adverse event will be summarized by treatment regimen.

Adverse events will be considered treatment emergent, if they first occurred or worsened at or after first application of study medication during the course of the study up to and including 7 days after last application of study medication.

Incidence of treatment emergent AEs (TEAEs), drug-related TEAEs, serious TEAEs, drugrelated serious TEAEs, as well as TEAEs leading to discontinuation will be summarized by primary system organ class and high level term by treatment regimen.

The definitions of incidence are as follows:

- Incidence of all events: # of subjects reporting the event with a start date during or after treatment/# of subjects valid for safety.
- Incidence of drug-related events: # of subjects reporting a drug-related event with a start date during or after treatment/# of subjects valid for safety.
- Incidence of events by maximum intensity: # of subjects reporting the event at the indicated intensity with a start date during or after treatment/# of subjects valid for safety.

Adverse events leading to death, premature discontinuation and serious adverse events will be listed. In this study, all AEs of urticarial, weight loss of > 20%, severe rash, and severe polyneuropathy will be considered AEs of special safety interest. Adverse events of special safety interest will be summarized by treatment regimen.

AEs occurring between the time of consent and the first dose of study drug will be summarized separately.

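### Urine discoloration from the placebo dye can arise only in the 30-day arm, and SAP 6.3 lets it add to that arm's TEAE and drug-related TEAE totals

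*Protocol*

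**What the plan says.** - Protocol 7.4: "Riboflavin is included as a colorant in the matching placebo tablets for study drug blinding purposes". It continues: "A common side effect of riboflavin ingestion is bright yellow urine". No rate is given.
- Protocol 7.1 gives the excipients of the nifurtimox tablets as "calcium hydrogen phosphate dehydrate, maize starch, silica colloidal anhydrous, and sodium lauryl sulfate". Riboflavin is not among them.
- Protocol 7.3 describes Treatment Group 2: "Nifurtimox tablets administered three times daily for 30 days, followed by nifurtimox placebo administered three times daily for 30 days". Treatment Group 1 takes active tablets throughout.
- Protocol 10.3.2.1, under Safety: "Subjects experiencing urine discoloration from riboflavin ingestion will be listed also, although these incidences will not necessarily be considered AEs".
- Protocol 9.6.1.1 defines an adverse event in general terms as an untoward occurrence, including "any unfavorable and unintended sign [including abnormal laboratory findings], symptom, or disease".
- SAP 6.3, Adverse Events, tabulates by regimen: "Incidence of treatment emergent AEs (TEAEs), drug-related TEAEs, serious TEAEs" and further categories. It does not mention riboflavin or urine colour, and it does not include the listing that the protocol promises.

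**The concern.** The discoloration is caused by a blinding excipient that only one arm receives. If some sites record it as an adverse event and others do not, the events recorded all fall in the 30-day arm, and how many there are depends on local habit.

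Reports are plausible. Families are told about urine colour in the consent form and at dispensing (Protocol 7.4). The Day 42 telephone contact, which falls in the placebo phase, uses a form that asks about new or changed symptoms and has a free field for other medical events (Protocol 16.1.1).

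At stake is how the overall safety lines are read side by side. A reader comparing the any-TEAE or drug-related TEAE percentage between 60 and 30 days would see a 30-day figure that may include a dye effect, and would have no total without it.

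**Working it through.** The plan states no figure on this point, so there is nothing to reproduce. The check is first a trace through the text, then an illustration under stated assumptions.

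**Trace**

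1. Source: riboflavin is in the placebo tablets (Protocol 7.4) and absent from the active-tablet excipients (7.1).
2. Who is exposed: only the 30-day arm, Days 31-60 (7.3).
3. Is it an adverse event? Protocol 10.3.2.1 leaves this open, and no current section says when it is one. The general definition in 9.6.1.1 leaves the decision to the investigator.
4. Is it inside the counting window? SAP 6.3 treats an event as treatment-emergent from the first dose until 7 days after the last study medication. Protocol 9.6.1.3 counts placebo as study medication in Part 1. So Days 31-60 are inside the window.
5. Is it excluded from any total? SAP 6.3 defines incidence as all subjects reporting the event, or a drug-related event, over subjects valid for safety. It makes no exception, and it does not restrict drug-related to nifurtimox.

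A recorded case therefore enters the any-TEAE total. If the investigator answers yes on causality, it also enters the drug-related total.

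**Illustration, any TEAE.** Let b be the proportion with another TEAE, d the proportion of the 30-day arm with discoloration, and r the share of those recorded as adverse events. With independence assumed:

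30-day proportion = b + (1 - b) × d × r; 60-day proportion = b

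The documents give none of b, d or r. All values below are assumptions.

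| b | d | r | Added, (1 - b) × d × r | 30-day | 60-day |
|---|---|---|---|---|---|
| any | any | 0 | 0 | b | b |
| 60% | 25% | 25% | 0.40 × 0.25 × 0.25 = 2.5 points | 62.5% | 60% |
| 40% | 50% | 50% | 0.60 × 0.50 × 0.50 = 15 points | 55% | 40% |
| 20% | 90% | 100% | 0.80 × 0.90 × 1.00 = 72 points | 92% | 20% |

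With the 100 children planned for the 30-day arm in Protocol 10.4, 15 points is about 15 children. The points themselves do not depend on arm size.

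**Illustration, drug-related TEAE.** Let f be the share of 30-day children whose discoloration is both recorded and judged drug-related, with an assumed 30% background. The added amount is f × (1 - 0.30):

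- f = 5%: 3.5 points
- f = 10%: 7 points
- f = 20%: 14 points

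The riboflavin contribution in the 60-day arm is 0 throughout.

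**After the change.** In totals that leave the event out, the added amount is 0 in both arms whatever r or f is.

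**The case against.** The case for leaving the plan alone has real substance.

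- *The analysis is descriptive.* SAP 6.3 specifies no formal testing of safety variables, and no decision rule uses these totals. This stands and limits the importance of the point.
- *The event would not be buried.* SAP 6.3 also breaks TEAEs down by system organ class and high level term, so a coded urine event would be visible there, apart from gastrointestinal or neurological events. This stands for the breakdown. It does not help the overall lines, which have no version without the event.
- *The protocol leans against counting it.* An expected, pre-announced colour change need not be unfavourable under 9.6.1.1. This is fair, but leaning is not a rule, and the SAP counts whatever sites record.
- *Causality may be answered no.* Protocol 9.6.1.2.3 asks for causality by study treatment and allows no where another explanation is highly likely. So the drug-related total may or may not be affected.
- *The sponsor has considered riboflavin.* The description of Amendment 1 calls the unblinding potential of urine colour unlikely to affect the safety evaluation significantly. That is amendment-log text about unblinding and does not address how the event is counted.

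Some stronger readings might be inferred, and the documents do not support them:

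- *That the rates will rise.* They can rise. A site that never records the event adds nothing, and a child with another TEAE adds nothing to the any-TEAE count.
- *That comparing the safety of the regimens is a secondary objective.* Protocol 4.1 concerns the safety profile of nifurtimox. The 30- versus 60-day objective there is serological. The comparison arises only because the tables are split by regimen.
- *That the listing would unblind the trial.* No section schedules it before unblinding.
- *That no 60-day child could report a colour change.* All families are warned, so unrelated reports are possible. The one-arm argument holds for riboflavin-caused discoloration only.

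**Conclusion.** The point holds as a gap in safety reporting. The plan, followed as written, can add dye-caused events to the any-TEAE and drug-related TEAE totals of the 30-day arm, with no matching source in the 60-day arm. The direction is fixed by the design.

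The size cannot be derived from the documents. Under the assumed values for any TEAE it runs from 0 to 72 points, and that width shows only that the plan does not control it. For the drug-related total the effect further requires that investigators attribute the colour change to study treatment, which is an assumption.

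A reader might go further and conclude that true 60-day toxicity would be hidden. The documents support only that a pooled line could be harder to read; the breakdown by organ class remains. The primary and secondary efficacy analyses are not touched. A short change to the SAP is justified because it removes a one-directional artefact at almost no cost.

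**What to change.** In SAP 6.3, Adverse Events, Part 1:

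- Show urine discoloration reported as an adverse event as its own row, by regimen.
- Present the any-TEAE and drug-related TEAE totals twice, with and without that event.
- Add the listing of subjects with urine discoloration that Protocol 10.3.2.1 promises, produced after unblinding.

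The cost is one extra row, a second set of totals and a few sentences in the SAP. No new data-collection item is needed, and the event need not be removed from the main totals. Because both versions are shown, a colour change truly caused by nifurtimox would still be visible. The listing can be only as complete as what sites recorded, but the totals without the event no longer depend on reporting habits.

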10.3.2.2 Part 2 (CHICO SECURE)

Analysis of the primary efficacy variable

The difference in the incidence rate of nifurtimox subjects with seronegative conversion (60-day regimen) and the rate estimated from historical data will be tested using a Poisson two-sided 95% exact confidence interval (CI).

The incidence rate of seronegative conversion for the primary efficacy variable will be modelled using a Poisson distribution with a 2-sided 95% exact CI. The rate will be estimated as the number of seronegative conversion divided by the time at risk of event (person-year) during the study. The rate of seronegative conversion () and a 2-sided limits (,) of the 95% CI for the rate can be calculated using the following formula [34]:

¹⁹¹ Modified as per amendment 2

¹⁹² Text modified/added for clarity as per Modification 2 (Amendment 1)

¹⁹³ Modified as per amendment 4

	Integrated Clinical Study Protocol BAY A2502/ 16027		
03 NOV 2020	Version 11.0	Page:	82 of 259

where n is the number of seronegative conversion observed , N the total subjects at risk in annual visit , V_i the th annual visit, the total number of visits, and are lower and upper confidence limits for the rate of seronegative conversion respectively, is the chi-square quantile for upper tail probability on v degrees of freedom.

This study uses an external control group of untreated patients with Chagas' disease in the 4year follow-up period presented in Sosa et al. [15, 35]. In the reference, seroconversion to a negative result in the placebo group after 4-year follow-up was detected in 2 subjects with conventional serology and in 0 subjects with IHA test. Thus, none of the subjects in the placebo group was considered as seroconverted by both test results. The person time at risk was on average 44 * 4 = 176 person years. The incidence rate estimate was 0% (0 / 176).

Superiority will be confirmed if the lower limit of the CI for the incidence rate of seronegative conversion for subjects in 60-day regimen is greater than the rate of historical placebo subjects with sero-conversion (i.e. 0 %).

No imputations will be made for missing data due to dropouts or other causes, as person-year is considered in the calculation of incidence rate.

Frequency counts and percentages of seronegative conversion will be provided by visit.

Missing data/drop outs

No imputations will be made for missing data due to dropouts or other causes. For the primary efficacy analysis done on the FAS, drop-outs will be included in the analysis using a Poisson distribution with person-year.

Analysis of the secondary and exploratory efficacy variables

The OD values from recombinant ELISA and total purified antigen ELISA will be analyzed descriptively. Changes from baseline will be summarized to show any serial reduction of OD. Baseline is defined as the OD values from the same ELISA tests measured at Visit 1 in part 1 of the study.

The proportion of subjects who show both seronegative conversion as confirmed by two assays (recombinant ELISA and IHA) and no evidence of established cardiomyopathy as measured by ECG will be calculated overall and by treatment regimen.

The proportion of subjects who show seronegative conversion as confirmed by nonconventional serology will be calculated overall and by treatment regimen.

The same method for calculating incidence rate and its 2-sided 95% CI will be applied on the following variables:

- Seronegative conversion as confirmed by two types of assay (recombinant ELISA and IHA) in subjects who were randomized and received at least one dose of the 30-day nifurtimox treatment regimen
- Seronegative conversion as confirmed by two types of assay (recombinant ELISA and IHA) in all subjects by age categories. The age categories are grouped as ≤2 years, >2

Version 11.0

03 NOV 2020

years to ≤ 6 years, >6 to ≤ 12 years, >12 to <18; age is defined as subject's age at randomization

• Seronegative conversion as confirmed by non-conventional serology in subjects who were randomized and received at least one dose of either 60- or 30-day nifurtimox treatment regimen

Analysis of the safety variables

Safety variables will be summarized by means of descriptive statistics and/or frequency tables as appropriate by treatment group.

AEs will be assessed by the investigator regarding their causal relationship to the administration of treatment and to any study procedure of the LTFU based on all information available. The results will be displayed in summary tables and listings as descriptive statistics.

10.4 Determination of sample size

Part 1 (CHICO)

This study uses historical controls estimated from cure rates presented in two publications [15][16]. The historical cure rates are as follows.

Publication	Age range	Sero-conversion rate (95%CI) in placebo patients
Andrade et al 1996	7-12	3/65 = 5% (1%,13%)
Sosa et al 1998	6 -12	2/44= 5% (1%,16%)

For the primary objective, superiority over placebo will be confirmed if the lower limit of the 95% CI for the nifurtimox (60-day regimen) cure rate is greater than 16%, the larger of the upper limits of the 95% CIs from the two publications.¹⁹⁴

According to Guhl et al [32], nifurtimox 12 month post treatment cure rate is about 55%, with a sample size of 200 for the 60-day regimen, the power is 99% for the lower limit of the 95% CI to be greater than 16%.¹⁹⁵

The number of subjects in the 30-day treatment regimen is based on the width of a 95% CI for the difference of two proportions. A sample size of 100 subjects for the 30-day subjects together with 200 subjects for the 60-day subjects will produce a CI with a half-width of approximately 0.12.

Part 2 (CHICO SECURE)

¹⁹⁴ Modified as per amendment 2

¹⁹⁵ Modified as per amendment 2

	Integrated Clinical Study Protocol BAY A2502/16027
03 NOV 2020	Version 11.0

Page: 84 of 259

According to Sosa-Estani [15, 35], the 48 months post treatment cure rate for benznidazole is about 5% as confirmed by two types of assay. For the primary objective, assuming a drop-out rate of 15%, the expected number of patients to be observed at the end of Part 2 (i.e., 48 months post treatment) in the 60-day regimen would be 170 out of the 200 patients in Part 1. Using the assumptions of 170 nifurtimox 60-day regimen patients in Part 2, a 5% cure rate, and that seronegative conversion events follow Poisson distribution, the estimated incidence rate is calculated to be 1.32% and the 95% CI of the incidence rate is (0.61%, 1.51%).

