10.1 General considerations

This study has been designed to focus on the efficacy and safety of treatment with nifurtimox in children diagnosed with Chagas' disease. In this study, approximately 300 pediatric subjects will be randomized (2:1 randomization, 60-day regimen vs. 30-day regimen). Subjects will be stratified by age into four strata. A minimum of 38 subjects in each age stratum is targeted, but not required, in order to be able to derive meaningful safety conclusions. Enrollment will continue until this specification is met, unless it is determined that such a target would be unlikely to be reached in a reasonable time.¹⁷⁹

Unless otherwise specified, all significance tests will be conducted using a 2-sided alpha level of 0.05, and CIs will be 2-sided 95% intervals. All variables collected in this study will be summarized with descriptive statistics at each assessment time. Subject disposition and demographic and baseline characteristics will be summarized descriptively for each treatment group. For continuous variables, descriptive statistics will include means, standard deviations, medians, minimums, and maximums. For categorical variables, frequency counts and percentages will be provided. These will be calculated for each age stratum by dose, as well as the overall set of study subjects.

No imputations will be made for missing values occurring in the safety and background variables. Treatment of missing values for efficacy variables is addressed later in this section.¹⁸⁰ Additional analyses may be specified in the SAP if missing data patterns observed during blinded review of the data suggest any possible bias.

Statistical analysis will be performed using Statistical Analysis System (SAS); the version used will be specified in the SAP.

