10.3.2 Statistical and analytical plans

10.3.2.1 Part 1 (CHICO)

Efficacy

Primary efficacy analysis

The difference in the proportion of nifurtimox subjects with sero-reduction¹⁸³ or sero-conversion (60-day regimen) and the proportion estimated from historical data will be tested using a 2-sided 95% CI for a single proportion.

The null hypothesis H_0 is $p_{nifurtimox} = p_{placebo}$

The alternative hypothesis H_1 is $p_{nifurtimox} \neq p_{placebo}$, where p_t is the sero-conversion rate for treatment t.

¹⁸³ Text modified for clarity (Amendment 1)

	Integrated Clinical Study Protocol
	BAY A2502/ 16027
03 NOV 2020	Version 11.0

Page: 80 of 259

Superiority will be confirmed if the lower limit of the CI for the proportion of nifurtimox subjects (60-day regimen) with sero-reduction or sero-conversion is greater than the proportion of historical placebo subjects with sero-conversion.¹⁸⁴

Sero-conversion for the historical placebo control is estimated as 16% from cure rates as presented in two publications [15][16], using a number greater than the larger of the upper limits of the 95% CIs from the two studies. Further details about the derivation of these rates are provided in Section 10.4.¹⁸⁵

Secondary and exploratory efficacy analyses ¹⁸⁶

A secondary analysis will be done to compare the proportion of subjects with sero-reduction or sero-conversion for the 60-day and 30-day nifurtimox regimens. This will be performed using a 2-sided 95% CI for the difference of two independent proportions.

The analyses specified above will also be done using data from the EOT visit, and 3 and 6 months after EOT.

The relationship of conventional serology results to qPCR results will be done using frequencies of matches and mismatches on the determination of disease status, and phi-correlation and kappa coefficient to assess the degree of agreement. The relationship of non-conventional serology to conventional serology will be analyzed in the same way.¹⁸⁷ The results from IHA and conventional serology will also be compared. The details of secondary and exploratory efficacy analyses will be further specified in the SAP.^{188,189}

Demographics and baseline characteristics

Demographics and baseline characteristics will be summarized by treatment and total population, using descriptive statistics and frequency tables as appropriate.

Safety

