#### Secondary analysis of the primary efficacy variable

A secondary analysis will be done to compare the proportion of subjects with sero-reduction or sero-conversion for the 60-day and 30-day nifurtimox regimens. This will be performed using an asymptotic 2-sided 95% CI for the difference of two independent proportions.

The null hypothesis  $H_0$  is  $p_{nifurtimox, 60d} = p_{nifurtimox, 30d}$ 

The alternative hypothesis H1 is  $p_{nifurtimox, 60d} \neq p_{nifurtimox, 30d}$ , where  $p_t$  is the cure rate for treatment *t*.

Difference in efficacy between the two groups will be confirmed if the CI for the difference of two proportions of nifurtimox subjects (60-day regimen *versus* 30-day regimen) with sero-reduction or sero-conversion does not include 0. The proportions and asymptotic 2-sided limits ( $l_l$ ,  $l_u$ ) of the 95% CI for *pnifurtimox*, 60d - *pnifurtimox*, 30d can be obtained by [3]

$$\begin{split} \hat{p}_{i} &= \frac{x_{i}}{n_{i}}, \qquad i = 1, 2. \\ l_{u} &= (\hat{p}_{1} - \hat{p}_{2}) + 1.96\sqrt{(\hat{p}_{1}(1 - \hat{p}_{1})/n_{1}) + (\hat{p}_{2}(1 - \hat{p}_{2})/n_{2})} + \frac{1}{2} \left(\frac{1}{n_{1}} + \frac{1}{n_{2}}\right) \\ l_{l} &= (\hat{p}_{1} - \hat{p}_{2}) - 1.96\sqrt{(\hat{p}_{1}(1 - \hat{p}_{1})/n_{1}) + (\hat{p}_{2}(1 - \hat{p}_{2})/n_{2})} - \frac{1}{2} \left(\frac{1}{n_{1}} + \frac{1}{n_{2}}\right) \end{split}$$

where  $p_i$ ,  $x_i$  and  $n_i$  denote the cure rate, the number of nifurtimox subjects with sero-reduction or sero-conversion, and the total number of subjects, for treatment *i* respectively. Treatment *i*=1, 2 represents 60-day and 30-day nifurtimox regimens, respectively.

The SAS code will be:

*Reference Number: BPD-SOP-060 Supplement Version: 6* 

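### The 0.12 half-width that sizes the 30-day arm is for an uncorrected interval; the continuity-corrected interval in the SAP gives about 0.13

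*Protocol*

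**What the plan says.** Protocol 10.4 (Part 1) gives precision as the only basis for the size of the shorter-regimen arm: "The number of subjects in the 30-day treatment regimen is based on the width of a 95% CI", meaning the interval that compares the two regimens. It names the numbers, "A sample size of 100 subjects for the 30-day subjects together with 200 subjects for the 60-day subjects", and claims that they "will produce a CI with a half-width of approximately 0.12". The ratio is fixed in protocol 10.1 ("2:1 randomization, 60-day regimen vs. 30-day regimen"), which also sets the error level: "all significance tests will be conducted using a 2-sided alpha level of 0.05, and CIs will be 2-sided 95% intervals". The only planning cure rate in 10.4 is for the 60-day regimen: "nifurtimox 12 month post treatment cure rate is about 55" per cent. Neither document gives a 30-day cure rate, a target difference or a power for this comparison.

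On the analysis, protocol 10.3.2.1 asks for the comparison "using a 2-sided 95% CI for the difference of two independent proportions" and mentions no continuity correction. SAP 6.2.1.1 (Secondary analysis of the primary efficacy variable) says: "This will be performed using an asymptotic 2-sided 95% CI for the difference of two independent proportions". The formula displayed there adds and subtracts ½(1/n₁ + 1/n₂) beyond the Wald limits, and the SAS code uses RISKDIFFC, the corrected option. The SAP will declare a difference in efficacy if the interval excludes zero.

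SAP 6.5 carries other figures for the same comparison: 260 and 130 children, and an interval width of about 20%.

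**The concern.** A sample-size statement based on precision should describe the interval that will be computed. Here the protocol's half-width appears to come from one interval and the SAP plans another. The SAP sentence says only that the interval is asymptotic. The correction appears in the formula and the code, so someone comparing the prose of the two documents would miss it.

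The half-width is the protocol's only stated justification for 100 children in the 30-day arm, and comparing the regimens is the first secondary objective of Part 1. If the figure is wrong for the planned analysis, the trial delivers a little less precision than it claims on its main randomised question. The test of the 60-day arm against 16% is not affected.

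**Working it through.** **Inputs.** n₁ = 200 and n₂ = 100 (protocol 10.4); two-sided 95% interval (protocol 10.1); 60-day cure rate 0.55 (protocol 10.4). The 30-day rate is not given. I assume 0.55 for the half-width, with 0.50 as the widest case, and vary it for power. Children with missing results at 12 months count as failures in the full analysis set (protocol 10.3.2.1), so the denominators stay at all treated children.

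**Step 1: reproduce the stated figure.** Uncorrected Wald half-width = 1.96 × √[p₁(1−p₁)/n₁ + p₂(1−p₂)/n₂].
- At 0.55 in both arms: 1.96 × √[0.55 × 0.45 × (1/200 + 1/100)] = 0.1194.
- At 0.50 in both arms: 0.1200.

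The stated 0.12 is reproduced without a correction.

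**Step 2: the SAP's interval.** The added term is ½(1/200 + 1/100) = 0.0075 on each side.
- At 0.55: 0.1194 + 0.0075 = 0.1269.
- At 0.50: 0.1200 + 0.0075 = 0.1275.

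The relative widening at 0.55 is 0.0075/0.1194 = 6.3%. To bring the corrected half-width down to 0.12 would take about 224 and 112 children at 0.55, or 226 and 113 at 0.50.

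**Step 3: coverage and type I error.** Full enumeration of two independent binomials, 0.55 in both arms:

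| Interval | Coverage | Rejects zero under the null |
|---|---|---|
| Corrected (SAP) | 96.1% | 3.9% |
| Uncorrected Wald | 94.6% | 5.4% |
| Newcombe, uncorrected | 94.6% | 5.4% |

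The normal approximation agrees for the corrected interval: 1.96 × 0.1269/0.1194 = 2.083, which corresponds to 96.3%. Over common rates from 0.20 to 0.80 in steps of 0.01, uncorrected Wald rejects 5.3% to 5.5% at every point. Newcombe exceeds 5% at 35 of the 61 points. The corrected interval never exceeds 5% (3.7% to 3.9%).

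**Step 4: power to exclude zero.** Exact, with the 60-day rate at 0.55:

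| 30-day rate (difference) | Uncorrected | Corrected | Loss, points |
|---|---|---|---|
| 0.50 (0.05) | 13.8% | 10.5% | 3.3 |
| 0.45 (0.10) | 38.8% | 32.7% | 6.1 |
| 0.43 (0.12) | 51.8% | 45.3% | 6.4 |
| 0.40 (0.15) | 70.6% | 64.9% | 5.7 |
| 0.39 (0.16) | 76.1% | 70.9% | 5.2 |
| 0.38 (0.17) | 81.0% | 76.4% | 4.5 |
| 0.35 (0.20) | 91.7% | 89.2% | 2.5 |
| 0.30 (0.25) | 98.8% | 98.3% | 0.5 |

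Newcombe has the same power as uncorrected Wald in each row.

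**Step 5: the SAP's own figures.** With 260 and 130 at 0.55, the half-width is 0.105 uncorrected (full width 0.21) and 0.110 corrected (full width 0.22). The SAP's 20% is thus a full width for a larger trial. It does not describe 200 and 100.

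**The case against.** The best defence is that the SAP's interval is a deliberate and conservative choice. The correction is displayed, referenced and coded, and it matches the primary analysis, which also uses a continuity correction (1/2n, BINOMIALC). It keeps the null rejection rate below 5%, whereas the obvious replacements run slightly above it at 55%. This stands, and it rules out calling the SAP's method an error.

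A second defence is that the protocol says only approximately, and names no 30-day rate. If the 30-day rate were 0.35 or 0.30 against 0.55, the corrected half-width would be 0.124 or 0.121, and either rounds to 0.12. That is true, but the protocol states no such rate. At the one rate it does state, used in both arms, the corrected figure is 0.127; at 0.50 it is 0.1275. The protocol's figure also agrees with the protocol's own description of the interval, so the mismatch lies between the protocol's planning figure and the SAP's formula.

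Three stronger readings are tempting, and the documents do not support them:
- *That the correction costs 5 to 6 points of power in general.* No alternative is stated, and the arm was sized on precision. The loss reaches that size only for true differences of about 0.10 to 0.16.
- *That the correction brings no gain in validity.* The rejection rates of 3.9% and 5.4% at 55% in both arms show a trade-off, and part of the power gap is the uncorrected interval's excess rejection.
- *That this is the only randomised efficacy comparison.* Protocol 4.1 also lists an exploratory 30- versus 60-day comparison by qPCR, and the SAP repeats the serology comparison at other visits.

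**Conclusion.** The stated half-width does not describe the planned interval. At 55% in both arms with 200 and 100 children, it should read 0.127 instead of 0.12: a gap of 0.0075, or about 6% of the half-width. The SAP's interval covers about 96% and is conservative, not invalid. The cost in power is at most about 6 points and depends on a true difference that the documents do not specify.

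The conclusion rests on the 55% rate applying to both arms. With a 30-day rate well below 55%, both intervals narrow and the corrected one can round to 0.12. The discrepancy is modest, but it concerns the one figure that the protocol offers for the size of the 30-day arm. The disagreement between SAP 6.5 and protocol 10.4 over sample size and width is larger. SAP 6.5 is also inconsistent within itself, since its Part 2 paragraph takes 200 children in the 60-day arm.

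**What to change.** In protocol 10.4, restate the half-width as about 0.13 and say that it is for the continuity-corrected interval with a 55% cure rate in both arms. In SAP 6.5, replace 260 and 130 with 200 and 100, and replace the 20% width with the same half-width. In SAP 6.2.1.1, say in words that the interval is continuity-corrected, so that the prose matches the formula and the code. These are text changes: no extra children and no change to the analysis.

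Replacing the correction with an uncorrected Newcombe interval is optional, and should be considered only if the Part 1 data are still blinded, which the documents do not settle. The mean Newcombe half-width at 55% in both arms is 0.117, so the protocol's 0.12 could then stay. The price is coverage of 94.6% to 95.0% in the scenarios run, in place of about 96%, and a null rejection rate of 5.4% instead of 3.9% at 55%. Once the data have been unblinded, the prespecified interval should be kept and only the figures restated.
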